3.2.2 Patient Population

The AFRS Study will include patients as specified in the Inclusion/Exclusion criteria. Study patients will have lateral, lateral recess and/or central stenosis at a single level from L3 to S1 requiring decompression and facetectomy. Detailed enrollment criteria can be found in the Patient Selection section of this Protocol.

Patients will receive either the investigational or control treatment, using a posterior approach through a midline incision to treat lateral, lateral recess and/or central canal stenosis. All patients will receive a decompression and complete facetectomy. The operative level will receive either the test or control treatment. Up to two adjacent additional levels may be treated through decompression as required to treat stenosis that does not result in complete facetectomy or fusion.

Patients randomized into the investigational group will receive the AFRS device. Those randomized to the control group will receive an instrumented posterolateral fusion.

If the assigned device cannot be placed in the patient during the surgical procedure, this patient will be considered a treatment failure. This patient should receive treatment at the discretion of the principal investigator and must be followed per the protocol through hospital discharge and/or the resolution of any procedure-related adverse events that have occurred.

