5.3 Operative Procedure

Following the surgery, details of the surgical procedure are documented including:

- Operative date, time, clinical site location, investigator performing surgery
- Treatment assigned, device used and traceability
- Vertebral levels treated, decompression performed, procedure and instrumentation time, blood loss
- Source of bone for fusion
- Antibiotics and/or deep vein thrombosis prophylaxis used pre-, intra-, and/or post-operatively, if applicable
- Intra-operative complications

Immediately following surgery, the patient is transported to the surgical recovery area and monitored according to the hospital/physician protocol for surgeries of this nature. The patient may be released from the recovery room to the nursing unit when s/he has met the

hospital's criteria for discharge from the recovery area. Immediate postoperative care will be dictated by the hospital or physician's standard care protocol regarding post-anesthesia recovery. Patients shall be encouraged to ambulate after surgery as soon as is medically reasonable.

Unforeseen events (findings or procedures) may occur during decompression/spinal preparation procedure(s) prior to implantation of the ACADIA® Facet Replacement System or Control System. These unforeseen events are those that are not planned as part of this surgery (eg, a drop in oxygen saturation intraoperatively, evidence of an acute myocardial infarction, allergic reaction to an antibiotic, etc). Unforeseen events that are emergent in nature should be recorded as AEs and the investigator should reassess the patient's suitability for continued participation in this study.

If an intraoperative decision is made to perform a procedure other than what was intended for study enrollment, the patient will be withdrawn from the study and will be followed for safety as a separate "Not Treated" cohort. If a randomized patient is withdrawn prior to treatment, the next patient will be assigned the next randomly determined treatment as per the study randomization plan until a sufficient number of patients have been treated per each group.

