8.0 STATISTICAL ANALYSIS PLAN

8.1 Analysis Populations

Primary Analysis Population:

The principal analysis of the primary and secondary endpoints will utilize the intent-to-treat (ITT) patient population. The ITT population will include all randomized subjects for whom surgery is attempted. Subjects for whom surgery is attempted but not successfully completed will be considered treatment failures. Randomized subjects in whom surgery is not attempted will be described in detail in a separate section of the study report.

Secondary Analysis Populations:

The primary and secondary objectives will be further analyzed using an as-treated (AT) analysis performed on all randomized subjects according to the treatment actually received.

The primary and secondary objectives will be further analyzed using a per protocol (PP) analysis performed on an evaluable patient population. The evaluable population will consist of all ITT subjects that: [1] meet critical study eligibility criteria and have no significant protocol deviations based on Clinical Events Committee assessment; [2] have the assigned procedure completed; and [3] completed the 24-month follow-up assessment.

Training Population:

This patient population will include all non-randomized AFRS treated patients enrolled during the pivotal phase of the trial as training cases at the site. A maximum of two patients per site for a total of 60 patients will be included in this cohort. Training cases will be described separately from randomized patients in the final study report and will be presented primarily using descriptive statistics. This patient population will be used to understand the learning curve in the use of the device by assessing the results of the Training cases relative to those obtained in the Treatment group arm of the randomized study.

An additional presentation of the safety data in which all of the patients treated with the AFRS device (non-randomized and randomized) are combined as one cohort and compared to the control group will be included.

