The leg pain VAS scores for subjects in each treatment group will be summarized separately by the more symptomatic and less symptomatic legs of each subject, as measured at baseline. For inference, the relevant hypothesis is

$$H: \mu_t - \mu_c < 0$$

where μ_t and μ_c are the average VAS scores for the more symptomatic legs (or less symptomatic legs, as appropriate) in the treatment and control groups, respectively.

Oswestry Disability Index (ODI)

The ODI scores for subjects in each treatment group will be summarized at the 3-, 6-, 12-, and 24-month time points. For the 24-month time point, a statistical test will be conducted. The relevant hypothesis is

$$H: \mu_t - \mu_c < \delta$$

where μ_t and μ_c are the average ODI scores in the treatment and control groups, respectively.

[REDACTED]

[REDACTED]

Adverse Events

All Adverse Events (AEs) will be tabulated and summarized as counts and percentages by treatment group. AEs will also be cross-tabulated separately according to treatment group and:

- Severity (Mild, Moderate, Severe)
- Seriousness (Serious, Non-serious)
- Device-Relatedness (Related, Not Related)
- Surgery-Relatedness (Related, Not Related)

In addition, the occurrence of any Unanticipated Adverse Device Effects (UADE) will be listed. The classification of severity, relatedness, and anticipated nature of AEs will be made by the Clinical Events Committee (CEC).

Summaries will include counts, percentages, and 95% Bayesian credible intervals for the difference in proportions between treatment groups. An analysis of safety outcomes which combines all AFRS treated patients (randomized and non-randomized) compared to control patients will also be performed. The statistical method for dichotomous outcomes (e.g., device-relatedness, surgery-relatedness) will be the Bayesian version of a comparison of proportions, described below. The statistical method for trichotomous outcomes (e.g., Severity) will be the Bayesian version of a comparison of polytomous outcomes, described below.

Surgical Revisions, Reoperations, Removals, and Supplemental Fixation

The incidence of a composite of surgical revisions, reoperations, removals, and supplemental fixation at the index level for subjects in each treatment group will be summarized at the 3-, 6-, 12-, and 24-month time points. For the 24-month time point, a statistical test will be conducted. The relevant hypothesis is

$$H: p_t - p_c < 0$$

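### The training population and pooled AFRS safety cohort are defined by being treated, ITT by attempted surgery, so aborted AFRS implantations can drop out of the learning-curve and pooled safety comparisons.

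*Combined protocol and SAP*

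**What the plan says.** Section 8.1 uses two tests for membership.

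- **ITT:** "The ITT population will include all randomized subjects for whom surgery is attempted". It adds: "Subjects for whom surgery is attempted but not successfully completed will be considered treatment failures".
- **Training cases:** "This patient population will include all non-randomized AFRS treated patients enrolled during the pivotal phase of the trial as training cases at the site". The set is meant to show the learning curve "by assessing the results of the Training cases relative to those obtained in the Treatment group arm of the randomized study". That sentence does not say which analysis set represents the randomized arm.
- **Pooled safety:** an additional presentation, described thus: "all of the patients treated with the AFRS device (non-randomized and randomized) are combined as one cohort and compared to the control group". The Adverse Events part of Section 8.7 repeats it: "An analysis of safety outcomes which combines all AFRS treated patients (randomized and non-randomized) compared to control patients will also be performed".

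Three other places bear on an aborted case.

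- Section 3.2.2: "If the assigned device cannot be placed in the patient during the surgical procedure, this patient will be considered a treatment failure".
- Section 4.0 allows removal from the study only where consent was withdrawn before treatment or treatment was never attempted. It also says that training cases are followed per protocol and analysed separately, with no condition that the device was implanted.
- Section 5.3 says that after an intraoperative decision to do a different procedure, "the patient will be withdrawn from the study and will be followed for safety as a separate" cohort labelled Not Treated.

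**The concern.** Failure to place the implant is a direct learning-curve outcome, and it is plausibly more frequent in a surgeon's first cases. A training set restricted to implanted patients cannot show it. If the randomized arm beside it still carries its own aborted cases as failures, the comparison tilts toward the training cases and understates the early-case problem it was set up to detect.

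The pooled safety presentation has a related weakness. An AFRS patient whose intraoperative complication prevented implantation is among those whose events matter most for safety. Selecting on completed implantation can remove that patient from the AFRS side.

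**Working it through.** **Step 1: reproduce the plan's figure.** Section 3.2.1 gives at most 30 sites and Section 8.1 at most two training cases per site: 30 × 2 = 60, which matches the stated cap.

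**Step 2: trace an aborted AFRS case through the sets.** *Treated* is taken here to mean that the device was implanted.

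| Set (Section 8.1) | Aborted randomized AFRS case | Aborted training case |
|---|---|---|
| ITT | In, scored as failure | Out, not randomized |
| As-treated | Classified by treatment received | Out, not randomized |
| Per protocol | Out, assigned procedure not completed | Out, not in ITT |
| Training | Out, randomized | Out, not treated |
| Pooled AFRS safety | Out, not treated | Out, not treated |
| Separate description of surgery not attempted | Out, surgery was attempted | Out, not randomized |

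The right-hand column has no entry that holds the patient. The Not Treated cohort in Section 5.3 is followed for safety, but no visible analysis in Section 8 uses it. This result follows from the wording of Section 8.1 and does not rely on Section 5.3.

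**Step 3: scale.** The documents give no abort rate, so q = 1%, 3% and 5% are assumptions. The randomized AFRS arm is 200 to 500 (Protocol Summary), so pooled attempts are 60 + 200 = 260 to 60 + 500 = 560.

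| Quantity | Formula | q = 1% | q = 3% | q = 5% |
|---|---|---|---|---|
| Training attempts absent | 60q | 0.6 | 1.8 | 3.0 |
| Chance of at least one | 1 − (1 − q)^60 | 0.45 | 0.84 | 0.95 |
| Pooled attempts absent, minimum size | 260q | 2.6 | 7.8 | 13.0 |
| of which randomized | 200q | 2 | 6 | 10 |
| Pooled attempts absent, maximum size | 560q | 5.6 | 16.8 | 28.0 |

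**Step 4: learning-curve shift.** Let r be the failure rate among completed implantations, assumed to be 20% or 40% and the same in both groups. An implanted-only set shows r. An attempted set that scores aborts as failures shows q + (1 − q)r. The gap is q(1 − r).

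- r = 20%: 0.8, 2.4 and 4.0 percentage points at q = 1%, 3% and 5%.
- r = 40%: 0.6, 1.8 and 3.0 points.

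Training cases would look better than the ITT arm by this amount with no real difference between them.

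**Step 5: pooled safety.** Assume an event in 10% of completed cases and in a share e of aborted cases. The attempted-set rate is 0.10(1 − q) + eq, against 10.0% in the treated-only set.

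- e = 50%: 10.4%, 11.2% and 12.0%.
- e = 100%: 10.9%, 12.7% and 14.5%.

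**The case against.** The strongest reply is that exclusion is inferred. The visible text never defines *treated*, and redacted text could. Sections 3.2.2 and 4.0 point toward keeping anyone in whom treatment was attempted, and Section 4.0 sets no implantation condition on training cases. This stands, and it limits the claim to the natural reading of an undefined term.

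A reader might go further in three ways that the documents do not support.

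- *Section 5.3 settles the meaning of treated.* Its Not Treated rule concerns a change to a procedure other than the one intended, and it comes after a paragraph on unforeseen events before implantation. Section 3.2.2 deals directly with a device that cannot be placed. The passages conflict, so Section 5.3 cannot serve as the definition.
- *The AFRS side is filtered and the control side is not.* Sections 8.1 and 8.7 do describe controls without the word treated, but the Section 5.3 context names both systems. If it governs, changed control procedures and changed randomized AFRS procedures are withdrawn too. One-sided filtering is established only as wording.
- *Aborted AFRS cases vanish from safety reporting.* Section 8.1 assigns the principal analysis of secondary endpoints, adverse events included, to ITT. At q = 5% and minimum size, 10 of the 13 absent pooled cases remain there. The 3 training cases have no named set, though Section 5.3 provides safety follow-up where it applies.

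The importance is also modest. The training presentation is mainly descriptive, the pooled one is supplementary, and no visible decision rule rests on either. With 60 and 200 patients at an assumed 70% success, the 95% half-width of the difference is 1.96 × √(0.21/60 + 0.21/200) ≈ 0.13, or about 13 points, well above the shifts in Step 4. That argues for modest weight. It does not justify leaving a systematic selection in place when wording can remove it.

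**Conclusion.** The point holds as a mismatch of definitions. On its natural reading, *treated* leaves an aborted training case without an analysis set and takes aborted randomized AFRS cases out of the pooled safety cohort, though not out of ITT.

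The learning-curve bias is conditional. It arises if the comparator is the ITT AFRS arm, which Section 8.1 does not say, and it then favours the training cases. The pooled presentation can understate AFRS events if aborted cases have more of them than completed cases.

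The actual size is unknown. Every rate used above is an assumption, and the results show scale only. The primary endpoint analysis does not use either set and is not affected. The change is worth making because it is cheap and removes selection on successful placement.

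**What to change.** 1. In Section 8.1, define the training population and the pooled AFRS safety cohort as all patients in whom the AFRS procedure was attempted, with *attempted* meaning the same as for ITT. Carry this into the Adverse Events part of Section 8.7.
2. Score uncompleted training cases as treatment failures, as in ITT.
3. Name the ITT AFRS arm as the learning-curve comparator.
4. Compare the pooled cohort with all control patients in whom surgery was attempted.
5. Reconcile the Not Treated withdrawal in Section 5.3 with Sections 3.2.2, 4.0 and 8.1, so that each aborted case has one stated place.

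The cost is a few sentences and no new procedures, since Sections 3.2.2 and 5.3 already provide for safety follow-up of these patients. AFRS figures may look slightly less favourable. Section 3.2.2 requires follow-up of a patient whose device could not be placed only to discharge and/or resolution of procedure-related events, so aborted cases may contribute less time than the 24 months of the others. Their safety data should be shown with their follow-up time.

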8.2 Primary Objective

The primary objective is to establish that AFRS (treatment) is non-inferior to fusion (control) at 24 months as assessed by subject success. [REDACTED]

8.3 Randomization, Sample Size, and Analysis Plan

This study is designed to adaptively determine the proper sample size. Possible sample sizes are 300, 450, 600, and 750 (maximum). Randomization will follow a 2:1 (treatment:control) allocation ratio and be stratified by site, using a blocked randomization scheme with blocks of randomly varying sizes. Further details on the randomization process are provided in **Section 5.2**.

In addition to the planned interim analyses that will determine the sample size, there will be several interim analyses conducted for the purpose of possibly declaring an early win. The first of these will occur when 300 subjects have completed 2 years of follow-up. If the trial does not stop for success at that analysis, a second analysis will occur when 450 have completed 2 years of follow-up. If the trial does not stop for success at that analysis, a final analysis will occur when the entire enrolled cohort has completed 2 years. It is not necessary for the trial to have stopped enrollment in order for the interim “Early Win” analyses to occur. For example, the first Early Win analysis (when 300 have completed 2 years) will occur even if the trial is still enrolling (i.e., the sample size determination algorithm has not determined the final sample size). Of course, if the final sample size is 300, there can be only 1 Win analysis (when the full cohort has reached 2 years); if the final sample size is 450, there can be only 2 Win analyses (when 300 have reached 2 years and when the full cohort has reached 2 years).

The sample size determination analyses and the “Early Win” interim analyses are triggered by different circumstances (number enrolled versus number completing 2 years) and are expected to follow different analysis schedules (i.e., although it is possible, a sample size analysis and an early win analysis are unlikely to occur simultaneously).

Further details on this analysis plan are given below.

Determination of Non-Inferiority and Superiority (“Win” Analyses)

Interim “Win” analyses are scheduled to occur when 300 and 450 subjects have completed 2 years of follow-up. A final analysis will occur when the entire enrolled cohort has completed 2 years of follow-up. At each of these analyses, the probability of non-inferiority $\Pr(H_{\delta=0.15} | \text{data})$ will be calculated, based on all observed data, including predicted 2-year outcomes for those subjects who have not reached 2 years.

[REDACTED]

[REDACTED]

[REDACTED]

[REDACTED]

Determination of Sample Size

The sample size is guided by a standard frequentist non-inferiority power analysis.

[REDACTED]

1 Farrington, C. P. and Manning, G. 1990. 'Test Statistics and Sample Size Formulae for Comparative Binomial Trials with Null Hypothesis of Non-Zero Risk Difference or Non-Unity Relative Risk.' *Statistics in Medicine*, Vol. 9, pages 1447-1454.
2 Hintze, J. (2004). *NCSS and PASS, Number Cruncher Statistical Systems*. Kaysville UT. www.ncss.com.
3 Jennison C and Turnbull BW, *Group Sequential Methods with Applications to Clinical Trials*. Boca Raton: Chapman & Hall, 2000, p 27, 30.

[figure not shown]
[REDACTED]

[REDACTED]

The sample size determination algorithm is thus defined as follows. When $N = N_i$ subjects are enrolled ($N_i = 300, 450, 600$), two predictive probabilities are calculated:

- $PP_{win} = \text{Pr}(\text{Eventual Win} \mid \text{Data}, \delta=0.10, N=N_i \text{ is the final sample size})$
- $PP_{fut} = \text{Pr}(\text{Eventual Win} \mid \text{Data}, \delta=0.15, N=750 \text{ is the final sample size})$

If PP_{win} exceeds a suitably high threshold W_i , subject accrual will stop because final success looks probable even using $\delta=0.10$. On the other hand, if PP_{fut} is less than a suitably low threshold F_i , subject accrual will stop and futility will be declared. If neither of these conditions obtains, enrollment will continue to the next larger sample size (450, 600, 750). Thresholds W_i and F_i are listed in **Table 8.3.1**. Further detail on the calculations of the predictive probabilities is given below under the heading “Predictions.”

8.4 Predictions

Predicted values of 2-year outcomes for those subjects who have not reached 2 years will be based on the intermediate outcomes measured at 6 months and 12 months. 3 month data will not be used in any of the predictive modeling. During this time, patients are continuing the post-operative healing process and may not be appropriate for this purpose.

At the time point of an interim analysis, there will be 4 types of subjects: subjects with complete 2-year data; subjects with 1-year data but no 2-year data; subjects with 6-month data but no 1-year or 2-year data, and subjects who have begun the study but do not yet have 6-month or 1-year data. For those with 6-month or 1-year interim data but no 2-year data, subjects will be considered to be one of the following:

- a) successes (i.e., meet all the criteria to be treatment successes, except that this is measured at 6 months or 1 year rather than 2 years)
- b) recoverable non-successes (i.e., do not meet the criteria to be successes, but it is still possible that they might become successes at 2 years)
- c) failures (i.e., subjects who cannot meet the definition of success at 2 years because of an event such as a device removal or re-operation.)

Subjects without 2-year follow-up data will thus be considered to be in one of 14 states (7 for each treatment group). The 7 states are:

- no interim data
- success at 6 months
- recoverable non-success at 6 months
- failure at 6 months
- success at 1 year
- recoverable non-success at 1 year
- failure at 1 year

Interim failures can be imputed to be failures at 2 years, with certainty. For each of the remaining 10 states (5 for each treatment group), the probability of becoming a success at 2 years is modeled via a Beta (a,b) prior distribution which is updated to a Beta($a+S$, $b+F$) distribution, based on the number S and F of subjects who went on from that state to become 2-year successes and failures, respectively. For example, if, in the treatment group at an interim analysis time point, 70 of 100 subjects with 2-year data are successes, and if 50 of the 70 two-year successes also met the definition of success at 1 year, then the transition probability from the 1-year success state to the 2-year success state will be modeled as Beta ($a+50$, $b+20$). At an interim analysis time point, any treatment-group subjects residing in the success-at-1-year-but-without-2-year-data state will have their 2-year outcome predicted on the basis of this Beta($a+50$, $b+20$) distribution. **Figure 8.4.1** graphically depicts the various transitions for a generic treatment group (treatment or control). The numerical example above would apply to transition #2 in the figure.

[figure not shown]
[figure not shown]

Figure 8.4.1. Graphical depiction of transitions from interim states (S = Success, R = Recoverable Non-Success, No Data) to 2-year Success. Each transition is assigned a Beta (a,b) prior distribution which is updated as data are gathered.

Prior Distributions for Transition Probabilities

The transitions of **Figure 8.4.1** are all assigned Beta(a,b) prior distributions. For “sample size looks,” the values of a and b are tabulated in **Table 8.4.2** and graphically depicted in **Figure 8.4.2**. These values represent the trial sponsor’s knowledge and belief about the relationship of the various interim states to the final state. At the times when sample size decisions must be made, the number of subjects who have completed 2 years (and thus provide information on the transition probabilities) will generally be insufficient to make good sample size decisions without including some additional information. Therefore, in all sample size determination analyses, the transitions are given informative priors, as tabulated in **Table 8.4.2**. However, for all “win looks,” only flat priors ($a = b = 1$) for the transitions will be used.

Table 8.4.2 Parameters for Prior Distributions of the Transition Probabilities used in the determination of sample size. For all "win" analyses, a and b are set to 1.

		Transition #				
		1	2	3	4	5
Parameter	a	411.97	386.55	229.80	204.00	234.50
	b	644.36	29.09	153.20	51.00	100.50

[figure not shown]

Figure 8.4.2 Prior Distributions of the Transition Probabilities used in the determination of sample size. For all "win" analyses, a and b are set to 1 for all transitions.

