Study Design:	
• Multi-center clinical trial at up to 30 investigational sites• Prospective, randomized, concurrently-controlled trial• Control: Instrumented posterolateral fusion• 200 Minimum/500 Maximum Investigational and 100 Minimum/250 Maximum Control patients using 2:1 randomization• Up to 60 non-randomized investigational training cases (two per site)
Study Duration/ Follow-up Period:	Study Duration: 48-58 months Follow-up: 6 week, 3, 6, 12 and 24 month postoperative time points, and annually thereafter as required by FDA
Indication for Use:	The AFRS Study will include patients who have lateral, lateral recess and/or central stenosis at the L3 to S1 level requiring decompression and facetectomy. The operative level will receive either the test or control treatment. Adjacent lumbar vertebrae levels may be treated through decompression as required to treat stenosis that does not result in complete facetectomy or fusion.
Inclusion Criteria	
• Is 21-85 years of age and skeletally mature;• Undergone at least six cumulative months of conservative treatment prior to surgery including any of the following: medications, NSAIDs, physical therapy, bracing, chiropractic manipulation, modified activities of daily living, epidural injections, facet block injections;• Lateral, lateral recess and/or central canal stenosis as demonstrated by compression of the thecal sac and/or cauda equina, nerve root impingement by either osseous or non-osseous elements or evidence of hypertrophic facets with encroachment into the central canal or lateral recess at the involved level as determined by MRI, CT scan, plain film or myelography;• Disc height measuring ≥ 4 mm at the operative level;• Persistent leg, thigh and/or buttock symptoms, including pain, numbness, burning or tingling with a minimum leg pain score of 40mm as measured with the Visual Analogue Scale (VAS) Index;• A score greater than 2 on a scale of 1-5 on the Zurich Claudication Questionnaire (ZCQ) Symptom Severity (SS) Score;• A score greater than or equal to 2 on a scale of 1-4 on the ZCQ Physical Function (PF) Score;• A candidate for a decompression with full facetectomy at the operative level;• A candidate for an instrumented posterolateral fusion;• Willing and able to comply with postoperative and routinely scheduled clinical and radiographic evaluations;• Lives in the immediate area and has no plans to relocate to another geographic

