3.3 Study Duration

It is anticipated that the overall duration of the pivotal phase of the AFRS study will be approximately 8 years. This estimate is based upon a projected patient enrollment period of 4-5 years, including the period of time (~2 years) under the previous sponsor, Facet Solutions. Follow-up visits will occur for the subsequent 24 months while all patients reach the 24 month postoperative time point, with data analysis and report generation accounting for an additional 4-6 months. The follow-up period may increase up to 10 years as needed to address postmarketing studies that may be required by the FDA during the approval process.

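### Do the tight priors at the sample-size looks make one futility threshold per look unreliable when accrual is uncertain?

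*Combined protocol and SAP*

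**What the plan says.** Section 8.3 (Determination of Sample Size) places looks at 300, 450 and 600 enrolled patients. At each look PP_fut is the predictive probability of an eventual win with margin 0.15 and a final N of 750. Accrual stops for futility if PP_fut "is less than a suitably low threshold" F_i. F_i carries the index of the look and nothing else.

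Section 8.4 states that "in all sample size determination analyses, the transitions are given informative priors", and it updates each transition only with patients who already have a 2-year outcome. Table 8.4.2 supplies the Beta parameters for these looks and presents them as the sponsor's "knowledge and belief about the relationship of the various interim states to the final state". It has no column for arm, and Figure 8.4.1 "graphically depicts the various transitions for a generic treatment group (treatment or control"), so one prior set appears to serve both arms. The same section explains that 2-year data will generally be too few at these looks to decide without added information, and it sets a = b = 1 for every win look.

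On timing, the Protocol Summary has "Study Duration: 48-58 months". Section 3.3 gives about 8 years in total and says "This estimate is based upon a projected patient enrollment period of 4-5 years".

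**The concern.** Looks are triggered by enrollment, but the priors move only with 2-year completers. With priors this heavy, the same true AFRS deficit gives a high PP_fut when accrual is fast and completers are few, and a much lower one when accrual is slow. One F_i per look cannot give the same stop rate in both situations, and the two durations leave the accrual rate unclear.

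Two harms seemed possible. Under fast accrual an AFRS that fails after month 12 might not be stopped, and each missed look enrolls 150 more patients, 100 of them on AFRS. Under slow accrual a device inside the margin might be stopped wrongly.

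**Working it through.** **1. The priors.** For a Beta(a, b), mean m = a/(a+b) and SD = sqrt(m(1−m)/(a+b+1)). From Table 8.4.2:

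| Transition | a + b | Mean | SD |
|---|---|---|---|
| 1 | 1056.33 | 0.39 | 0.0150 |
| 2 | 415.64 | 0.93 | 0.0125 |
| 3 | 383.00 | 0.60 | 0.0250 |
| 4 | 255.00 | 0.80 | 0.0250 |
| 5 | 335.00 | 0.70 | 0.0250 |

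In reverse, these round means and SDs return every a and b to two decimals. The weights therefore appear to come from chosen SDs rather than patient counts. At N=300 there are only about 200 AFRS patients in all.

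**2. The plan's example.** Section 8.4 supposes that "50 of the 70 two-year successes also met the definition of success at 1 year" and adds: "The numerical example above would apply to transition #2 in the figure". With the printed counts of 50 and 20, the sample-size look predicts (386.55+50)/(415.64+70) = 0.90, the win look predicts 51/72 = 0.71, and the prior keeps 415.64/485.64 = 86% of the weight. This shows the weight and no more. As worded, the 20 are 2-year successes, so 50 of 70 is not an observed transition rate.

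**3. Accrual rates that fit Section 3.3.** Enrollment of 48-60 months means that N=450 needs at least 450/60 = 7.5 per month and N=600 at least 600/60 = 10. The fastest rate is 750/48 = 15.6. Rates of 5 or 6.25 per month do not reach these looks within that period. Completers are N − 24 × monthly rate, two thirds of them AFRS:
- N=450: 270 in total (180 AFRS) at 7.5; 150 (100) at 12.5; about 75 (50) at 15.6.
- N=600: 360 (240) at 10; 300 (200) at 12.5; about 225 (150) at 15.6.

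**4. The other timeline.** The summary's 48-58 months, less 24 of follow-up and 4-6 of reporting, leaves 48−24−6 = 18 to 58−24−4 = 30 months of enrollment. That is 10-16.7 per month for 300 patients and 25-42 for 750. Reaching a look by month 30 leaves at most 450 − 24×15 = 90 completers at N=450 and 600 − 24×20 = 120 at N=600, so the timelines do differ.

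**5. Futility stop rates.** Simulated with Table 8.4.2 in both arms at the accrual rates of step 3. Assumed: win threshold 0.95; F from 0.05 to 0.20; fusion at 70% following the prior means; uniform accrual; no loss to follow-up; transitions other than #2 identified by their means; patients not yet enrolled predicted from the no-data transition; early-win looks and accrual stops for PP_win ignored.

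| Look | Monthly rate | AFRS 50%, deficit after month 12 |
|---|---|---|
| 450 | 7.5 | about 12-39% |
| 450 | 12.5 | 0-2% |
| 450 | 15.6 | 0% |
| 600 | 10 | about 44-71% |
| 600 | 12.5 | 23-50% |
| 600 | 15.6 | 4-19% |

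With AFRS 10 points worse, stops occur in at most about 2% of trials at N=450 and 8% at N=600. With flat priors and the same F values they occur in about 12-33% and 16-35%.

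**6. When wrong stops become frequent.** Suppose F is tuned at 12.5 per month to stop 10% of trials with AFRS 10 points worse, and is then applied across the feasible rates. The stop rate runs from 31% to 1% at N=450 and from 16% to 4% at N=600. That tuning needs F of about 0.77 and 0.44, meaning futility declared while a win is still 77% or 44% likely. This does not fit a threshold described as suitably low, and the tuning rule is not the plan's.

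**The case for a change.** The best case for a change is that the priors worsen a problem that could be milder. If F is tuned as in step 6, flat priors hold the stop rate for a 10-point deficit fairly steady across accrual (9-13% at N=450 and 9-15% at N=600, even over a range down to 5 per month), while the tabulated priors do not. If F is low instead, a device 20 points worse through late failure is almost never stopped at N=450 once accrual reaches 12.5 per month. Indexing F by completers would cost one table and a rerun of existing simulations.

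The arithmetic stands, and so does the insensitivity to late deficits. The case for a change is weaker. PP_fut also varies with completers under flat priors: in one simulated case at N=600 with AFRS 20 points worse, its mean falls from 0.65 with no completers to 0.02 with 467. The tight priors also bring a gain. With F matched at 12.5 per month, they stop deficits visible by month 12 in 95% of trials at N=450 and 98% at N=600, against 67% and 79% with priors cut to a weight of 30. With no completers at a look, no threshold finds a late deficit: at 26.8 per month, matched F stopped only 6-9% of late 20-point deficits. There the limit is missing information.

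**Conclusion.** No change to the plan follows. The priors are as heavy as they look, and the futility rule's sensitivity to late failure does depend on accrual. At low F the consequence is limited to continued enrollment of an inferior device, 100 AFRS patients per missed look. Wrongful stopping of a device 10 points worse stays at or below about 2% (N=450) and 8% (N=600). Final inference is untouched because every win look uses flat priors.

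Section 8.4 states the choice of informative priors and its reason, and it is a fair trade-off: less reaction to late deficits in return for better detection of early ones and fewer wrong stops. It cannot be shown that F_i was set for a single accrual rate. The values in Table 8.3.1 are not visible, and Section 8.5 (Operating Characteristics) is in the contents but absent from the public copy. Indexing F by completers would be another defensible design, not a correction.

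The two durations should be reconciled as a clerical matter. Section 3.3 counts the roughly 2 years under the previous sponsor, so it is probably the current text and the summary line a leftover; that is an inference. It would be natural, when doing so, to confirm that the simulations behind F_i cover the expected accrual and deficits arising after month 12. The stop rates rest on the assumptions listed in the working. Only the prior moments and the timeline arithmetic come straight from the documents.
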